² Screening laboratory tests include: ALT, AST, creatinine (and calculate an estimated glomerular filtration rate (eGFR) the formula used is determined by the sites, but should be consistent throughout the study), and urine or serum pregnancy test for females of child-bearing potential. Laboratory tests performed as part of routine clinical care in the 48 hours prior to enrollment will be accepted for determination of eligibility.

³ Baseline assessments should be performed prior to first infusion. Laboratory tests performed as part of routine clinical care in the 24 hours prior to first dose will be accepted for the baseline safety laboratory tests. Baseline may be the same as the screening laboratory tests if obtained in the 24 hours prior to first dose.

⁴ Safety laboratory tests include WBC with differential, hemoglobin, platelets, creatinine, total bilirubin, ALT, AST, and INR.

⁵ Any laboratory tests performed as part of routine clinical care within the specified visit window can be used for safety laboratory testing. ⁶ In-person visits are preferred but recognizing quarantine and other factors may limit the subject's ability to return to the site for the visit. In this case, the visit may be performed by phone.

- If still hospitalized at Day 15 and 29 or returns for an in-person visit: assess adverse events, collect clinical data, vital signs, safety laboratory tests, and research laboratory samples (OP swab and blood) as able.
- If phone call only on Days 15 and 29 and all Day 22 and Day 60 visits: assess adverse events, clinical status (ordinal scale), readmission to a hospital, and mortality only.

⁷ Oropharyngeal swabs are preferred, but if these are not obtainable, saliva or nasopharyngeal or nasal swabs may be substituted. ⁸ Pre-dose serum sample collections for PK and immunogenicity.

⁹ To include markers of inflammation and coagulation: CRP, ferritin, fibrinogen, d-dimer.

¹⁰ Day 8, 22 and 60 visits performed by phone call or home visit if discharged from the site hospital: assess adverse events, clinical status (ordinal scale), readmission to a hospital, and mortality only.

¹¹ Only collected at selected sites capable of processing.

¹² Steroids and other concomitant therapies intended as specific treatment of COVID-19, as well as all biologics, will be assessed from 7 days prior to enrollment to Day 29. All other concomitant medications will be assessed from 7 days prior to enrollment to Day 15 or upon discharge, whichever comes first.

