3.3.2. Analysis Visit Windows

The nominal visit as recorded in the electronic data capture (EDC) or within the permitted visit window as specified by the Schedule of Assessments will be used when data are summarized by visit (see [Table 1](#) and [Table 2](#)). Any data relating to unscheduled visits will not be assigned to a particular visit or time point. However, the following exceptions will be made:

- An unscheduled visit prior to the first dose of study product may be included in the calculation of baseline value, if applicable.

Table 1: Clinical Status Study Day Windows

Analysis Visit Day	Nominal Day	Target day	Visit Window
Screening	Screening	-1 to 1	<1
Baseline	Day 1 (Hospitalized)	1	1
Day 3	Day 3 (Hospitalized)	3	3
Day 5	Day 5 (Hospitalized)	5	5
Day 8	Day 8 (Hospitalized)	8	8
Day 8	Day 8 (Discharged)	8	6-10
Day 11	Day 11 (Hospitalized)	11	11
Day 15	Day 15 (Discharged)	15	13-17
Day 22	Day 22 (Discharged)	22	19-25
Day 29	Day 29 (Discharged)	29	26-32
Day 60	Day 60 (Discharged)	60	57-63

Table 2: Lab Sample Collection Study Day Windows

Analysis Visit Day	Nominal Day	Target day	Visit Window
Screening	Screening	-1 to 1	<1
Baseline	Day 1 (Hospitalized)	1	1
Day 3	Day 3 (Hospitalized)	3	2-4*
Day 5	Day 5 (Hospitalized)	5	4-6*
Day 8	Day 8 (Hospitalized)	8	7-9
Day 11	Day 11 (Hospitalized)	11	10-12
Day 15	Day 15 (Hospitalized)	15	14-16
Day 15	Day 15 (Discharged)	15	13-17
Day 29	Day 29 (Hospitalized)	29	28-30
Day 29	Day 29 (Discharged)	29	26-32

*For windows that overlap, the priority will be given to the earlier date. For example, a lab sample drawn on Study Day 4 will be used as a Study Day 3 lab sample draw if there isn't a lab sample drawn for Study Days 2 or 3, regardless of whether a Study Day 5 lab is drawn.

In general, the Study Day 1 (baseline) value will be the last non-missing value prior to the administration of the first dose. If multiple measurements occur on the same day, the last non-missing value prior to first dose will be considered as the baseline value. If these multiple measurements are recorded on Day 1 but the time is

not available, the average of these measurements (for continuous data) will be considered the Study Day 1 value. For categorical measurements, if there are multiple records with the same time or no time recorded on the same day prior to the first dose, the value with the lowest severity will be selected as baseline (i.e., normal will be selected over abnormal).

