13. Days of hospitalization from date of admission by Study Day 29.	Primary	
 If a subject is discharged and no further hospitalization data are available, consider the subject as not readmitted, no additional imputed days will be added. If a subject dies while hospitalized, the number of days of hospitalization will be imputed as the number of days between the date of admission and the expected date of subject's Study Day 29 visit+1.
	Subgroup	
 Use complete data for ordinal score to define this endpoint.

Endpoint	Analysis	Imputation Method
Other Secondary Endpoints: Safety		
1. Values of CRP, ferritin, D-dimer, LDH, and fibrinogen on Study Day 1: Study Days 3, 5, 8, 11,15 and 29	Primary	
 If results are not available for any visit day(s) but are available for visits before or after that visit, the average of the two nearest visits will be imputed for all missing visits between them. If a subject dies or is otherwise terminated early from the study, their last available observation will be carried forward. If baseline is missing, another pre-treatment dose will be used, or the earliest post treatment dose will be used.
2. 14-day Mortality	Primary	
 Subjects whose last assessment in the study is before Day 13 (beginning of Day 29 window) and before death will be considered not dead and censored at the date of their last observed assessment. Subjects who complete follow-up will be censored at Day 15. Deaths that occur after Day 15 will be censored at Day 15.
	Primary with Sensitivity Imputation	
 Subjects whose last assessment in the study is before Day 13 (beginning of Day 15 window) and were discharged to a location other than LTAC, hospice care or other hospital, or subjects died after Day 15 will be considered non-events and censored at Day 15. Subjects whose last assessment in the study is before Day 13 (beginning of Day 15 window) and before death and without being discharged to a location other than LTAC, hospice care or other hospital at their last assessment will be considered non-events and censored at the date of their last observed assessment. Subjects who complete follow-up will be censored at Day 15.

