For analyses based on multiple imputation, remaining missing ordinal scores will be imputed for Day 8 using the PROC MI procedure in SAS. Treatment group (trtvar), baseline ordinal score (basesteroidusevar), baseline steroid use (basesteroidvar), duration of symptoms prior to randomization (dursymp), age, indicator for black or Hispanic ethnicity (blackhispl), presence of 2 or more comorbidities (comorb2fl), baseline CRP (basecrp), and indicator for discharge to a location other than long term care facility (LTAC), hospice care or another hospital (i.e., good discharge status) at the last assessment of the subject being imputed will be included as covariates in the multiple imputation model for ordinal scores at each timepoint using monotone logistic regression. The good discharge status variable at last assessment variable (goodischstat) will vary from subject to subject and will be defined as the discharge status for all subjects at the last assessed timepoint of the subject being imputed. For example, if the subject being imputed had their last assessment at Day 5, the good discharge status variable for all subjects will be defined as their discharge status at Day 5. The timing for the discharge status variable will be defined according to the last assessment timepoint of the subjects being imputed. The treatment group variable (trtvar) represents the randomized treatment group. Each imputation model will include all subjects with complete data plus all subject with missing ordinal score at Day 8 to be imputed who have the same last assessment day. The procedure will loop through all possible last assessment days (i.e., day 1 through day 8) imputing data for subjects missing data who were last assessed on the same day.

Since missing data in any of these baseline characteristics may cause issues with the monotone missing data patterns, the following methods will be used to fill in missing baseline covariates data:

- For continuous baseline covariates (age, CRP, duration of symptoms), mean imputation will be used to replace missing values with the overall mean value from all randomized subjects for the given covariate.
- For indicator variables of baseline steroid use, black or Hispanic ethnicity, and presence of two or more comorbidities, subjects with missing values will be given the value with the greatest number of subjects among all randomized subjects.
- We do not anticipate any missing data for actual baseline ordinal score.

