9.6. Clinical Laboratory Evaluations

Clinical safety laboratory AEs are collected Study Days 1, 3, 5, 8, and 11 (while hospitalized); and outpatient Study Days 15 and 29 (if attends in-person visit or still hospitalized). Parameters evaluated include WBC, differential, Hgb, PLT, creatinine, (and calculate an estimated glomerular filtration rate (eGFR); the formula used is determined by the sites, but should be consistent throughout the study), total bilirubin, AST, ALT, and INR. Additional laboratory parameters may be summarized based on each intervention's safety profile. Laboratory safety parameters will be graded according to the NIAID Division of AIDS (DAIDS) Table for Grading the Severity of Adult and Pediatric Adverse Events, Corrected Version 2.1 (July 2017).

The distribution of Grade 3 and 4 chemistry and hematology laboratory results by maximum severity, time point, ordinal score and treatment group will be presented in [Table 62](#) through [Table 66](#) for chemistry and [Table 76](#) through [Table 81](#) for hematology. Absolute values and change from baseline of laboratory values will be summarized by mean, SD, median, minimum, and maximum results at Study Days 1, 3, 5, 8, 11, 15 and 29 in [Table 57](#), through [Table 61](#) for chemistry and [Table 67](#) through [Table 75](#) for hematology. Individual laboratory results are provided in [Listing 27](#) for chemistry and hematology and [Listing 29](#) for urine pregnancy results.

Markers of inflammation and coagulation results for CRP, ferritin, d-dimer, LDH, and fibrinogen will be summarized by mean, SD, median, minimum, and maximum results at Study Day 1 and Study Visit (not necessarily actual) Study Days 3, 5, 8, 11, 15 and 29 by treatment as well as change from baseline at each post-Study Day 1 visit ([Table 82](#)). Figures with mean and SD over time will also be presented by treatment ([Figure 31](#), [Figure 32](#), [Figure 33](#), [Figure 34](#), [Figure 35](#)). Individual results for markers of inflammation are presented in [Listing 28](#).

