N=Number of subjects in the Safety population. n= Number of unique subjects that satisfies the row criteria.									
^a Severity as per NIAID Division of AIDS (DAIDS) Table for Grading the Severity of Adult and Pediatric Adverse Events, Corrected Version 2.1 (July 2017).									

Tables with similar format:

Table 77: Platelets Results by Baseline Ordinal Score, Severity and Study Days — Safety Population

Table 78: Hemoglobin Results by Baseline Ordinal Score, Severity and Study Days — Safety Population

Table 79: INR Results by Baseline Ordinal Score, Severity and Study Days — Safety Population

Table 80: Neutrophils Results by Baseline Ordinal Score, Severity and Study Days — Safety Population

Table 81: Lymphocytes Results by Baseline Ordinal Score, Severity and Study Days — Safety Population

Table 82: Summary of Continuous Markers of Inflammation and Immune Response by Study Day — Safety Population

Study Day	Immune Response Measure	Treatment A (N=X)						Treatment B (N=X)					P-value ^a
		n	Mean	SD	Median	Min	Max	Mean	SD	Median	Min	Max	
Day 3	C-reactive protein	xx	x.x	x.xx	x.x	x	x	x.x	x.xx	x.x	x	x	0.xxx
	Ferritin	xx	x.x	x.xx	x.x	x	x	x.x	x.xx	x.x	x	x	0.xxx
	D-Dimer	xx	x.x	x.xx	x.x	x	x	x.x	x.xx	x.x	x	x	0.xxx
	Fibrinogen	xx	x.x	x.xx	x.x	x	x	x.x	x.xx	x.x	x	x	0.xxx
	LDH	xx	x.x	x.xx	x.x	x	x	x.x	x.xx	x.x	x	x	0.xxx
Rows should be repeated for Study Days 1, 5, 8, 11, 15, and 29													

SD= Standard Deviation. Min= Minimum. Max= Maximum. N=Number of subjects in Safety population.
 Values of D-Dimer reported as <220 were analyzed as 219 and values of CRP reported as <3.0 were analyzed as 2.9.
^a P-value of tests of two sample means.

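### SAP Table 7 lets a post-treatment sample stand in for a missing baseline CRP or other marker, which distorts change from baseline for those subjects

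*SAP*

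**What the plan says.** The row of SAP Table 7 for the inflammation and coagulation markers gives two fallbacks in order: "If baseline is missing, another pre-treatment dose will be used, or the earliest post treatment dose will be used". This is current text, not part of the change log.

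Elsewhere baseline is pre-dose:

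- SAP 3.3.2: "In general, the Study Day 1 (baseline) value will be the last non-missing value prior to the administration of the first dose". The one widening it names is still pre-dose: "An unscheduled visit prior to the first dose of study product may be included in the calculation of baseline value, if applicable".
- Protocol 1.2, footnote 3 to the schedule: "Baseline assessments should be performed prior to first infusion".

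Baseline marker values are used in several places:

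- SAP 9.6 summarises the markers by treatment at each visit, "as well as change from baseline at each post-Study Day 1 visit".
- The Table 82 shell has rows for every study day including Day 1, with a p-value column footnoted "P-value of tests of two sample means".
- Baseline CRP is a continuous covariate in the main model for survival without respiratory failure, a key secondary endpoint, and in the Cox model for time to ventilation or death (SAP 6.4.2 and Table 6).
- CRP below 150 mg/L defines a subgroup in Table 6 and helps select the Table 42 population (SAP 8.2.2).

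SAP 6.5.2 has a separate rule for missing CRP, written for the Day 8 multiple imputation model: "mean imputation will be used to replace missing values with the overall mean value from all randomized subjects for the given covariate".

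**The concern.** The drug is given once, on Day 1, and Protocol 4.2.2 expects exposure to begin quickly. The next scheduled draw is Day 3, with an analysis window of Days 2 to 4 (SAP Table 2). A value from that draw can already carry drug effect and disease course.

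If it is labelled baseline, the subject's change at that visit is the value minus itself. Every later change is measured from a point after the early response. A value taken after randomisation and dosing is also reported as Day 1, where the arms should differ only by chance.

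At stake is the marker change-from-baseline evidence. A proof-of-concept trial of an anti-inflammatory agent would use it to judge biological activity. There is also a gap next to the clause: no rule says what to do when baseline CRP is missing as a covariate or for the CRP<150 cut-off. A programmer could reach for the Table 7 rule.

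**Working it through.** The plan states no figure on this point, so there is none to reproduce. The check compares the texts and then sizes the effect.

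**Texts side by side.** Table 7 acts when the baseline is missing. Its first fallback, another pre-treatment value, is consistent with SAP 3.3.2 and the protocol footnote. Its second is not: both of those places describe only pre-dose values, and neither refers to an exception in Table 7.

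**Inputs.**

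- *m*, the share of subjects with no pre-dose marker value: not in the documents; assumed 5% to 20%.
- *d*, the true arm difference at the first post-dose draw, in SD units: not in the documents; assumed 0.3 to 0.5.
- Missingness is taken to be unrelated to arm or marker level, and the affected subjects' first post-dose draw to be Day 3.

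**Formulas.** An affected subject has the Day 3 value as baseline, so:

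- expected arm difference at baseline = *m* × *d* (it should be 0);
- expected arm difference in Day 3 change = (1 − *m*) × *d* + *m* × 0 = (1 − *m*) × *d*;
- expected arm difference in change at a later visit with true effect *d_t* = *d_t* − *m* × *d*.

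**Results (SD units).**

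| *m* | Baseline difference, *d* = 0.3 | Baseline difference, *d* = 0.5 | Day 3 change difference, *d* = 0.3 | Day 3 change difference, *d* = 0.5 |
|---|---|---|---|---|
| 5% | 0.015 | 0.025 | 0.285 | 0.475 |
| 10% | 0.03 | 0.05 | 0.27 | 0.45 |
| 20% | 0.06 | 0.10 | 0.24 | 0.40 |

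The Day 3 difference in change falls by the fraction *m*. Later visits lose the fixed amount *m* × *d*. For example, with *m* = 10%, *d* = 0.3 and a later effect of 0.5, the result is 0.5 − 0.03 = 0.47, a loss of 6%.

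A simulation agrees. At *m* = 10% and *d* = 0.5, the arm differences averaged −0.052 at baseline and −0.449 in Day 3 change (negative because the drug lowers the marker), against −0.05 and −0.45 by formula.

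With pre-dose values only, the expected baseline difference is 0 and the full *d* is kept.

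**If the same value were also used as the CRP covariate.** In a simulated logistic model with *d* = 0.5, the treatment odds ratio moved toward 1: from 0.79 to 0.81 at *m* = 10%, and from 0.78 to 0.83 at *m* = 20%. These figures depend on the simulation model, and the plan does not say that the value is used this way.

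**The case against.** The post-treatment value is a last resort, tried only after any other pre-treatment value. Unscheduled pre-dose values count, and Protocol 8.1.2 accepts routine-care laboratory results from the 24 hours before first dose. The number affected may be very small. With no drug effect on the marker, the rule creates no expected arm difference. SAP 3.3.2 opens with a general qualifier, so the sponsor could call Table 7 an exception. All of this stands and limits the size. It does not make a post-dose value a sound baseline.

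Three stronger readings are tempting, and the documents do not support them.

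- *That the marker p-values are biased by the diluted change.* The Table 82 tests compare values at a visit, and Tables 44 and 45 list marker values; none tests change. Tables 44 and 45 are also optional. A substituted baseline alters the Day 1 row and, at most, a later value filled by averaging neighbouring visits. Observed later values are untouched.
- *That Table 7 contradicts the overall-mean rule in SAP 6.5.2.* That rule fills covariates for the Day 8 multiple imputation model. It is a different rule for a different purpose.
- *That treatment will influence the CRP covariate or who enters the CRP<150 analysis.* Table 7 is organised by endpoint. The rows for survival without respiratory failure and for time to ventilation or death do not contain this fallback. The plan also has a sensitivity model without CRP (SAP 6.4.2) and repeats the Table 42 analysis in all mITT subjects (Table 43).

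**Conclusion.** The point holds, within limits. The clause is inconsistent with the plan's general pre-dose baseline and with the protocol's pre-infusion baseline. Followed as written, it damages the change-from-baseline summaries in SAP 9.6 and the Day 1 row of Table 82.

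The arm difference in change at the first post-dose visit shrinks by about the share of subjects with no pre-dose value: 5% to 20% under the assumed range, and negligible if almost nobody lacks one. The direction is toward no effect.

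The Day 8 primary analysis is not affected. Its model has no CRP covariate, and its imputation model has its own rule for missing CRP.

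For the CRP-adjusted key secondary analysis and the CRP<150 population, the documents show only a missing rule. Carry-over is a risk to close off, not an established fault.

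**What to change.** 1. In the marker row of SAP Table 7, delete the post-treatment fallback and replace dose with value. Use pre-dose values only. If there is none, leave baseline and change from baseline missing.
2. State that any baseline CRP used as a covariate or for the CRP<150 cut-off must be pre-dose.
3. Where CRP is a covariate, extend the overall-mean rule of SAP 6.5.2 to it explicitly.
4. Where CRP<150 defines the subgroup or the Table 42 population, leave out subjects with no pre-dose CRP. They remain in Table 43.

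The cost is one deleted clause and a few clarifying sentences. Subjects with no pre-dose value drop out of the change-from-baseline summaries. With about 200 subjects, the assumed 5% to 20% would be 10 to 40 (0.05 × 200 and 0.20 × 200), so the number left out should be reported by arm.

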6.5.2. Multiple Imputation

Multiple imputation will be performed for the primary endpoint of the Day 8 ordinal score for subjects whose last assessment in the study is before Day 8 and missing ordinal scores after their last assessment for the following two scenarios:

- For the primary analysis of the primary endpoint, assign a score of 2 for subjects missing Day 8 score after last assessment for subjects with a good discharge status (i.e., discharged to a location other than LTAC, hospice care, other hospital) at last assessment and use multiple imputation to impute missing data at Day 8 only for subjects without a good discharge status (i.e., subjects with no post baseline data or still hospitalized or those discharged to LTAC, hospice care, or other hospital) at their last assessment

- As a sensitivity analysis of the primary endpoint, use multiple imputation to impute missing ordinal scores for all subjects missing Day 8 ordinal scores after last assessment regardless of their good discharge status at last assessment.

For analyses based on multiple imputation, remaining missing ordinal scores will be imputed for Day 8 using the PROC MI procedure in SAS. Treatment group (trtvar), baseline ordinal score (basesteroidusevar), baseline steroid use (basesteroidvar), duration of symptoms prior to randomization (dursymp), age, indicator for black or Hispanic ethnicity (blackhispl), presence of 2 or more comorbidities (comorb2fl), baseline CRP (basecrp), and indicator for discharge to a location other than long term care facility (LTAC), hospice care or another hospital (i.e., good discharge status) at the last assessment of the subject being imputed will be included as covariates in the multiple imputation model for ordinal scores at each timepoint using monotone logistic regression. The good discharge status variable at last assessment variable (goodischstat) will vary from subject to subject and will be defined as the discharge status for all subjects at the last assessed timepoint of the subject being imputed. For example, if the subject being imputed had their last assessment at Day 5, the good discharge status variable for all subjects will be defined as their discharge status at Day 5. The timing for the discharge status variable will be defined according to the last assessment timepoint of the subjects being imputed. The treatment group variable (trtvar) represents the randomized treatment group. Each imputation model will include all subjects with complete data plus all subject with missing ordinal score at Day 8 to be imputed who have the same last assessment day. The procedure will loop through all possible last assessment days (i.e., day 1 through day 8) imputing data for subjects missing data who were last assessed on the same day.

Since missing data in any of these baseline characteristics may cause issues with the monotone missing data patterns, the following methods will be used to fill in missing baseline covariates data:

- For continuous baseline covariates (age, CRP, duration of symptoms), mean imputation will be used to replace missing values with the overall mean value from all randomized subjects for the given covariate.
- For indicator variables of baseline steroid use, black or Hispanic ethnicity, and presence of two or more comorbidities, subjects with missing values will be given the value with the greatest number of subjects among all randomized subjects.
- We do not anticipate any missing data for actual baseline ordinal score.

Twenty imputation sets will be generated, and final results from these 20 imputed datasets will be aggregated.

Pseudocode:

- Define `ordscore_d8` as the ordinal score:
- DEFINE `ordscore_d8` as the ordinal score value at Day 8.
- DEFINE `j`: as the last time assessment for the subjects being imputed used to define the good discharge status variable in the model. Possible values for `j` are from 1 to 8.
- DEFINE `jMax`= Maximum time of last assessment observed during the study.
- DEFINE `g&j`=analysis dataset containing predictors and ordinal score for complete data subjects as well as subjects missing Day 8 score who were last assessed on the same day.
- DEFINE `&&modelVars` = list of covariates to be used in the imputation model: `trtvar baseordscorevar basesteroidusevar dursymp age blackhispl comorb2fl basecrp goodischstat_j`.

- DEFINE imp_g&j = g&j with 20 imputed values for the missing ordinal score added by PROC MI.

```
%do j=1 %to &jMax;
```

```
proc mi data=g&j out= imp_g&j impute=20 seed = 300&j noprint;
  class trtvar baseordscorevar basesteroidusevar blackhispfl comorb2fl
  goodischstat_j ordscore_d8;
  var trtvar baseordscorevar basesteroidusevar dursymp age blackhispfl comorb2fl
  basecrp goodischstat_j ordscore_d8;
  monotone logistic(ordscore_d8 = trtvar baseordscorevar basesteroidusevar dursymp
  age blackhispfl comorb2fl basecrp goodischstat_j);
run;
  %end;
```

imp_g&j will be subset to contain only rows for the subjects with imputed ordinal scores and merged together with data from subjects with complete data to form twenty complete multiply imputed datasets. The final dataset imp_g will contain 20 replicates for complete subjects and data from the 20 imputation datasets for imputed subjects.

Proportional Odds analysis with multiple imputation:

The following SAS pseudocode will be used to perform the proportional odds analysis with treatment, baseline ordinal score and baseline steroid use as covariates to generate the treatment odds ratio, p-value, and predicted probabilities of the ordinal scale levels by treatment and ordinal score using data from multiple imputation:

```
proc logistic data=imp_g out=imp_parms plots(only)=effect(x= ordscore_d8
  sliceby =baseordscorevar*trtvar individual connect);
  by _imputation_;
  class baseordscorevar (param=ref ref=5) basesteroidusevar (param=ref ref=no
steroid use) trtvar (param=ref ref=placebolabel);
  model ordscore_d8 = trtvar baseordscorevar basesteroidusevar;
  oddsratio trtvar;
  ods output oddsratioswald = orest parameterestimates=pars;
run;
```

```
*Keep only estimates for the treatment variable;
```

```
data pars1;set pars;where Variable='Treatment variable';run;
```

```
*Combine estimates;
```

```
PROC MIANALYZE DATA=pars1;
  ODS OUTPUT PARAMETERESTIMATES= logor;
  MODELEFFECTS estimate ;
  STDERR stderr ;
```

```
RUN;
```

```
*Transform estimates from the log(OR) scale to the OR scale;
```

```
data OR;
  SET logor;
  OR_estimate = EXP(ESTIMATE);
  OR_LCL_95 =OR_estimate*EXP(-1.96*STDERR);
  OR_UCL_95 =OR_estimate*EXP(+1.96*STDERR);
  OR_LCL_80 =OR_estimate*EXP(-1.28*STDERR);
  OR_UCL_80 =OR_estimate*EXP(+1.28*STDERR);
```

```
RUN;
```

Similar pseudocode for odds ratio between the binary progression strata will use used for the Day 8 ordinal score endpoint analyzed by proportional odds using multiple imputation.

If the primary analysis results are at least borderline significant with a p-value < 0.10 and more than 5% of subjects have missing primary endpoint data, additional analyses will be performed to evaluate the effect of the missing data assumptions on the results. Using a tipping point strategy, these analyses will vary the Day 8 ordinal score independently across groups to determine if there is a distribution of missing data that would result in a change of conclusion.

